bimekizumab-SS-1mL	1mL bimekizumab safety syringe
BMI	body mass index
CDMS	clinical data management system
CI	confidence interval
CRO	contract research organization
ECG	electrocardiogram
eCRF	electronic Case Report form
FAS	Full Analysis Set(s)
FAS-a	Full Analysis Set for the bimekizumab-AI 1mL
FAS-s	Full Analysis Set for the bimekizumab-SS-1mL
GCP	Good Clinical Practice
ICF	Informed Consent form
ICH	International Council for Harmonisation
IEC	Independent Ethics Committee
IFU	instructions for use
IL	interleukin
IMP	investigational medicinal product
IRB	Institutional Review Board
IRT	interactive response technology
PFS	prefilled syringe
PK	pharmacokinetic(s)
PKS	Pharmacokinetic Set
PKS-a	Pharmacokinetic Set for the bimekizumab-AI-1mL
PKS-s	Pharmacokinetic Set for the bimekizumab-SS-1mL
PS	Patient Safety
PsA	psoriatic arthritis
Q4W	every 4 weeks
SADE	serious adverse device effect

SAE	serious adverse event
SAP	Statistical Analysis Plan
sc	subcutaneous
SFU	safety follow-up
SIAQ	Self-injection Assessment Questionnaire
SOP	Standard Operating Procedure
SS	Safety Set(s)
SS-a	Safety Set for the bimekizumab-AI-1mL
SS-s	Safety Set for the bimekizumab-SS-1mL
USADE	unanticipated serious adverse device effect
VAS	visual analog scale

PUBLIC COPY
This document cannot be used to support any marketing authorization application and any extensions or variations thereof.

1 SUMMARY

DV0004 is a Phase 3, multicenter, open-label, randomized, noncomparator, North America and Europe substudy to PA0012 in adult subjects with active psoriatic arthritis (PsA) to evaluate the safe and effective use of 2 single-use disposable self-injecting device presentations for the subcutaneous (sc) administration of bimekizumab solution (the investigational medicinal product [IMP]). To provide patients with PsA with options for the self-administration of bimekizumab, DV0004 will evaluate 2 investigational self-injecting device presentations, which are drug product (IMP) associated with a functional secondary packaging: the 1mL bimekizumab safety syringe (bimekizumab-SS-1mL) and the 1mL bimekizumab auto-injector (bimekizumab-AI-1mL).

DV0004 is a substudy of PA0012, which is a multicenter, open-label, long-term safety study for subjects with PsA who complete 1 of the Phase 3 feeder studies (PA0010 or PA0011). The PA0012 study will evaluate the long-term safety, tolerability, and efficacy of bimekizumab in subjects with PsA, and study personnel qualified in sc injection technique will administer bimekizumab to subjects (except for specified study visits at which subjects may self-administer) in a 1mL True North prefilled syringe (referred to throughout this protocol as the 1mL PFS). Subjects will begin the DV0004 substudy and the PA0012 study at the same time. The DV0004 substudy will include all PA0012 study assessments from Baseline to Week 4 (inclusive). However, subjects in the DV0004 substudy will self-administer bimekizumab at Baseline and at Week 4.

During the 4-week Treatment Period of DV0004, subjects will receive bimekizumab 160mg every 4 weeks (Q4W). This dose regimen will remain stable for the entire 4-week Treatment Period of DV0004 (consistent with PA0012). In the DV0004 substudy, subjects will be randomly assigned to 1 of the 2 self-injecting device presentations and will self-administer bimekizumab at Baseline and at Week 4. A safety follow-up (SEU) telephone call will occur 1 week after the last self-administration in DV0004 (Week 5). After Week 5 in the DV0004 substudy, subjects will continue in PA0012 (the next visit after DV0004 completion will be the Week 8 Visit in PA0012). At Week 8 in PA0012, study personnel qualified in sc injection technique will administer bimekizumab to subjects in a 1mL PFS, or the subject/caregiver/appropriate designee will perform administration under the supervision of the site staff after training.

To compensate for subjects who have different study treatments between the feeder studies and DV0004, DV0004 is planned to enroll approximately 200 subjects (100 subjects per device presentation arm) to ensure that approximately 50 subjects per device presentation arm are evaluable for steady state trough pharmacokinetic (PK) level analyses. Within each device presentation arm, subjects will be divided into tertiles by body mass index (BMI); there will be approximately 33 subjects per tertile, which is expected to yield approximately 16 to 17 subjects per tertile who are evaluable for steady state trough PK level analyses.

The primary objective of the DV0004 substudy is to evaluate for each self-injecting device presentation the ability of subjects with PsA to safely and effectively self-inject bimekizumab 4 weeks after training in self-injection technique using the bimekizumab-SS-1mL or the bimekizumab-AI-1mL. The primary outcome variable is the percentage of subjects able to self-administer safe and effective injections using the bimekizumab-SS-1mL or the bimekizumab-AI-1mL at Week 4.

Safe and effective self-injection will be evaluated by the study personnel and is defined as:

- Complete dose delivery: Subject self-injects the complete dose of bimekizumab as confirmed by a visual inspection of the bimekizumab-SS-1mL or the bimekizumab-AI-1mL, which shows that the IMP is delivered completely (ie, container is empty), and
- No adverse device effects (ADEs) that would preclude continued use of the device presentation for self-injection (ie, no serious adverse device effects [SADEs] and/or ADEs leading to withdrawal from the DV0004 substudy)

The secondary study objectives and other study objectives are provided in Section 3.2 and Section 3.3, respectively. Of note, one of the other study objectives is to assess trough PK levels associated with self-injection using the test device presentation, injection by study personnel using the 1mL PFS, injection site (abdomen or thigh), and BMI category (by tertile). The secondary outcome variable, other outcome variables, and the other safety variable are listed in Section 4.1.2, Section 4.1.3, and Section 4.1.3.4, respectively.

2 INTRODUCTION

Psoriatic arthritis is a common, chronic inflammatory disease characterized by a series of linked cellular changes in the skin. Bimekizumab (UCB4940; the IMP) is an engineered, humanized full length monoclonal antibody of immunoglobulin G1 subclass that selectively and potently inhibits the activity of interleukin (IL)-17A and IL-17F in vitro. Interleukin-17A and IL-17F are key proinflammatory cytokines believed to play important roles in autoimmune and inflammatory diseases. Bimekizumab is being developed for the treatment of patients with inflammatory diseases such as PsA, psoriasis, and axial spondyloarthritis.

It is important for patients who may use bimekizumab for the treatment of active PsA to have options for the self-injection of bimekizumab that fit their needs and preferences. Whilst some patients may prefer to manually regulate various tasks comprising the self-injection process (eg, needle visibility of skin penetration by needle, control speed of self-injection), others may prefer a more automated process (eg, do not wish to see the needle, desire an automatic injection). UCB therefore intends to provide patients with two different options to self-inject bimekizumab.

The DV0004 study is a substudy of the PA0012 study. PA0012 will evaluate the long-term safety, tolerability, and efficacy of bimekizumab in subjects with PsA; study personnel will administer bimekizumab in a 1mL PFS (except at specified study visits at which subjects may self-administer). The DV0004 substudy will evaluate 2 self-injecting device presentations: the 1mL bimekizumab-SS-1mL and the 1mL bimekizumab-AI-1mL. Subjects will begin the DV0004 substudy and the PA0012 study at the same time. The DV0004 substudy will include all PA0012 study assessments from Baseline to Week 4 (inclusive). However, subjects in the DV0004 substudy will self-administer bimekizumab at Baseline and at Week 4.

In the DV0004 substudy, the self-injecting device presentations are drug product (IMP) associated with a functional secondary packaging (either the bimekizumab-SS-1mL or bimekizumab-AI-1mL). The bimekizumab-SS-1mL and the bimekizumab-AI-1mL are each single integral units which are intended exclusively for use in the given combination and are not reusable. Therefore, compliance to the EU Medical Device Regulation (except for Annex 1) and European Conformity marking (CE marking) is not foreseen. Full descriptions of the 2 devices are provided in Section 7.1.1 and Section 7.1.2, respectively.

The proposed study is planned to demonstrate that adult subjects with PsA can safely and effectively self-inject bimekizumab using the bimekizumab-SS-1mL or the bimekizumab-AI-1mL.

3 STUDY OBJECTIVES

3.1 Primary objective

The primary objective of the study is to evaluate for each self-injecting device presentation the ability of subjects with PsA to safely and effectively self-inject bimekizumab 4 weeks after training in self-injection technique using the bimekizumab-SS-1mL or the bimekizumab-AI-1mL.

3.2 Secondary objective

The secondary objective of the study is to evaluate the ability of subjects with PsA to safely and effectively self-inject bimekizumab immediately after training in self-injection technique using the bimekizumab-SS-1mL or the bimekizumab-AI-1mL.

3.3 Other objectives

Other objectives of the study are to evaluate the following:

- Subject experience of self-injection as assessed by the pain visual analog scale (VAS) for injection site pain and the Self-injection Assessment Questionnaire (SIAQ)
- Trough PK (trough bimekizumab) levels associated with self-injection using the test self-injecting device presentations, injection by study personnel using the 1mL PFS injection site (abdomen or thigh), and BMI category (by tertile)
- Immunogenicity of bimekizumab associated with self-injection using the self-injecting device presentations and injection by study personnel using the 1mL PFS
- The structural and mechanical integrity of the bimekizumab-SS-1mL and the bimekizumab-AI-1mL after completion of self-injection
- The functional integrity of the bimekizumab-SS-1mL and the bimekizumab-AI-1mL after completion of self-injection
- The overall safety and tolerability of self-injections using the self-injecting device presentations

4 STUDY VARIABLES

4.1 Outcome variables

4.1.1 Primary outcome variable

The primary outcome variable is the ability to self-administer safe and effective injections using the bimekizumab-SS-1mL or the bimekizumab-AI-1mL at Week 4. Safe and effective self-injection will be evaluated by the study personnel and is defined as:

- Complete dose delivery. Subject self-injects the complete dose of bimekizumab as confirmed by a visual inspection of the bimekizumab-SS-1mL or the bimekizumab-AI-1mL which shows that the IMP is delivered completely (ie, container is empty), and
- No ADEs that would preclude continued use of the device presentations for self-injection (ie, no S.ADEs and/or ADEs leading to withdrawal from the DV0004 substudy).

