7.6 Drug and device presentation accountability

The Investigator will receive numbered treatments that will be assigned to eligible subjects by an IRT at Baseline. All IMP administrations will be observed by the Investigator or his/her appropriately trained designee.

Appropriate accountability forms that reflect the receipt and use of the IMP and the device presentations will be supplied to the investigational site. Details of any loss of the self-injection device presentations due to breakage or wastage, non-use, destruction at the study site, or return to the Sponsor or designee must also be recorded on these forms. All supplies and pharmacy documentation must be made available throughout the study for UCB (or designee) to review.

The Investigator (or designee) is responsible for retaining all used, unused, and partially used IMP and device presentations until returned to UCB. Used or partially used devices are to be stored at room temperature in a secured area and may only be destroyed following UCB's instruction. Devices with noted deficiencies (see Section 11.1.1.3) are to be returned to UCB immediately. The Investigator may assign some of the Investigator's duties for drug accountability at the study site to an appropriate pharmacist/designee.

The IMP and device presentations intended for the study cannot be used for any other purpose than that described in this protocol.

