11.1 Primary outcome variable

The primary outcome variable is the percentage of all subjects able to self-administer safe and effective injections using the given device at DV0004 Week 4. Safe and effective self-injection will be evaluated by the study personnel as defined below:

- Complete dose delivery: Subject self-injects the complete dose of bimekizumab as confirmed by a visual inspection of the bimekizumab-SS-1mL or the bimekizumab-AI-1mL which shows that the IMP is delivered completely (i.e., the container is empty), and
- No ADEs that would preclude continued use of the device presentations for self-injection (i.e., no SADEs and/or ADEs leading to withdrawal from the DV0004 substudy).

All data to assess the primary outcome is collected on the subject self-injection of bimekizumab CRF page for DV0004 Week 4. For the number of subjects with safe and effective self-injections simply the cases which indicated “yes” for the question “Did the subject self-inject the complete dose of Bimekizumab” and “no” for the question “Were there any AEs related to use of the investigational device for self-injection” at DV0004 Week 4 are counted.

The number and percentage of subjects with safe and effective self-injections will be tabulated separately for each device presentation using the relevant FAS population (FAS-s or FAS-a). The 90% CIs based on the Exact Binomial method will be reported as well. The number and percentage of subjects with safe and effective self-injections is tabulated for each device presentation by COVID-19 enrollment period, as described in Section 4.9.1.

Assessments where the self-injection was not performed by the subject will not be included in any summary statistics.

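### The Week 4 success definition does not say whether a prompted or partly helped injection counts as self-injection, and injections taken over by staff leave the summary instead of counting as failures.

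*Protocol*

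**What the plan says.** Protocol 3.1 sets the primary objective as "the ability of subjects with PsA to safely and effectively self-inject bimekizumab 4 weeks after training in self-injection technique". Protocol 5.1 and Table 5-1 place training at Baseline and list none at Week 4.

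Protocol 4.1.1 leaves the judgement to site staff ("Safe and effective self-injection will be evaluated by the study personnel and is defined as") and gives two conditions. The first is "Subject self-injects the complete dose of bimekizumab as confirmed by a visual inspection of the bimekizumab-SS-1mL or the bimekizumab-AI-1mL". The second is "No ADEs that would preclude continued use of the device presentations for self-injection", explained there as no SADE and no ADE leading to withdrawal from the substudy. SAP 2.2.1.1 repeats both.

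SAP 11.1 turns this into a count of two answers from the self-injection CRF page at Week 4: yes to "Did the subject self-inject the complete dose of Bimekizumab" and no to "Were there any AEs related to use of the investigational device for self-injection". It then adds: "Assessments where the self-injection was not performed by the subject will not be included in any summary statistics". SAP 11.2 applies the same rule and the same exclusion at Baseline.

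On the setting, Protocol 7.6 states: "All IMP administrations will be observed by the Investigator or his/her appropriately trained designee". Protocol 7.7 places the injections in the clinic.

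**The concern.** Because training is scheduled four weeks earlier and not repeated, the Week 4 visit tests retained skill. The sign that the skill has been lost is that the subject needs help. The definition does not deal with help: there is no condition that the injection be unaided, and no statement of how much help stops it being a self-injection. A trained person is present at every injection, and no passage tells that person to stay silent.

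The study is estimation only (Protocol 14.2), so the percentage and its interval are the result. Protocol 5.4 expects most commercial users to self-inject. That they will usually do so without trained staff beside them is an inference, but a natural one. If prompted injections count as successes and taken-over injections disappear, the reported figure describes observed, possibly prompted, self-injection. A reader would take it as ability to self-inject.

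**Working it through.** **1. How SAP 11.1 classifies each situation at Week 4** (no device-related AE throughout):

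| Situation | Classification as written | Against counting only unaided injections as success |
|---|---|---|
| Unaided, full dose | Success | No difference |
| Verbally prompted, full dose | Success: the subject injected and the container is empty | Percentage higher |
| Partial physical help, full dose | Open: yes gives success, no gives failure, or treated as not performed by the subject and excluded | Higher, unchanged, or higher |
| Prompted, dose incomplete | Failure | No difference |
| Taken over by staff | Excluded from numerator and denominator | Percentage higher |

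Where the rule makes a difference, the difference is upward.

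**2. Inputs for an illustration.** The plan has no figure on this point to reproduce. From the documents: about 100 subjects per arm (Protocol 5.1.2) and exact binomial 90% intervals (Protocol 14.3.1, SAP 11.1). Assumed: 97 counted successes, and the numbers prompted or taken over. The documents support none of these assumed values.

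**3. Formulas.** Let n be the subjects who attempt the injection, s the counted successes, h the prompted subjects among them, and t the taken-over injections.

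- Reported percentage: s / (n − t)
- Unaided percentage: (s − h) / n
- Exact 90% limits for x of N: the 5% point of Beta(x, N − x + 1) and the 95% point of Beta(x + 1, N − x)

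**4. Prompting only** (n = 100, s = 97, t = 0). The reported value is 97/100 = 97.0% (92.4 to 99.2), whatever h is.

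- h = 0: unaided 97/100 = 97.0% (92.4 to 99.2)
- h = 2: unaided 95/100 = 95.0% (89.8 to 98.0)
- h = 5: unaided 92/100 = 92.0% (86.0 to 96.0)

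Each prompted subject is worth 1/100 = 1 percentage point.

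**5. Takeover only** (n = 100: 97 successes, 1 failure, 2 taken over).

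- Reported: 97/(100 − 2) = 97/98 = 99.0% (95.3 to 99.9)
- Takeovers kept as non-success: 97/100 = 97.0% (92.4 to 99.2)
- Difference: 97 × 2 / (100 × 98) = 194/9800 = 2.0 percentage points

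**The case against.** **Self-performance is already required.** A reader might infer that success is only an empty container, so that any assisted subject counts. The documents do not support that. The first condition and the CRF question both ask whether the subject self-injected; the empty container only confirms that the dose was complete. Staff who gave hands-on help may answer no, which is a failure. For the same reason it goes too far to say that needing help can never lower the percentage: a no answer lowers it, and so does an incomplete dose despite prompting. What remains is that verbal prompting passes both conditions and that partial physical help is left to each site.

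**Staff are given an observing role.** Where the protocol intends administration under staff supervision after training, it says so for Week 8 (Protocol 5.1), and it does not use that wording for Week 4. Inclusion criterion 3 also asks for a subject judged able to use the device according to its instructions. Both points make coaching less likely. Neither excludes it or says how to classify it.

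**Help may be recorded elsewhere.** The eCRF, its completion guidelines, the instructions for use and the training materials are not among the documents reviewed. The exclusion in SAP 11.1 presupposes some record of who injected. It is therefore unverified that help goes unrecorded. Even if it is recorded, SAP 11.1 counts only the two answers quoted above.

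**This is a design choice, and the size is assumed.** Both are true. The definition agrees between protocol and SAP, there is no hypothesis or threshold to cross, and no document gives a rate of help. The SIAQ confidence and ease-of-use scores bear on perceived competence, but not on help actually given.

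**Baseline differs.** Injection follows training at the same visit, so prompting is hard to separate from instruction. This stands, and it limits the proposal to Week 4.

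**Conclusion.** The point holds as a gap in definition with a one-sided effect. For the Week 4 outcome, a prompted subject who delivers the full dose is a success, a partly helped subject is classified by site judgement, and a subject whose injection staff take over is removed instead of being counted as a failure. Compared with a count of unaided injections, each can raise the percentage.

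The size is unknown. If 0 to 5 of 97 counted successes among 100 subjects were prompted, the overstatement is 0 to 5 percentage points; two takeovers removed from the denominator add 2.0 points in the separate example. These rest on assumed counts and an arm of 100. They do not show that help occurred.

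The documents do not support the wider conclusions that every assisted injection is a success, that help can only raise the result, or that the trial fails to collect information on help.

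**What to change.** 1. In Protocol 4.1.1 and SAP 2.2.1.1 and 11.1, require for Week 4 success that the subject completed the injection without verbal prompting or physical help from study personnel. This governs how an injection is classified, not whether staff may step in.
2. Record help on the existing self-injection CRF page as none, verbal, physical or taken over, if it is not already there.
3. Amend the exclusion sentence in SAP 11.1 so that Week 4 injections attempted by the subject but completed or taken over by staff stay in the denominator as non-success.
4. Show the numbers of helped and taken-over injections beside the composite, by device.
5. At Baseline (SAP 11.2), report help descriptively and leave the success definition unchanged.

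The cost is one CRF item, a short change to the definition in both documents, one changed SAP sentence and possibly a slightly lower reported percentage. Help has to be recorded prospectively. SAP Amendment 3 already followed data cleaning, so if the Week 4 visits are complete and help was not captured, items 1 and 2 cannot be applied. In that case the number of excluded injections should still be shown, with a sensitivity count that treats attempted but taken-over injections as non-success where the records identify them. The conclusion should then be worded as self-injection under observation, with prompting not ruled out.

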4.1.2 Secondary outcome variable

The secondary outcome variable is the ability to self-administer safe and effective injections using the bimekizumab-SS-1mL or the bimekizumab-AI-1mL at Baseline (the first self-injection visit, immediately after training in self-injection technique). Safe and effective self-injection will be evaluated by study personnel and is defined using the same criteria as the primary outcome variable (see Section 4.1.1).

4.1.3 Other variables

4.1.3.1 Outcome variables

The other outcome variables are:

- Responses to pre-injection SIAQ (versions 2.0 and 2.1) at Baseline
Whenever SIAQ is assessed, version 2.0 of the SIAQ will be used to assess bimekizumab-SS-1mL and version 2.1 of the SIAQ will be used to assess bimekizumab-AI-1mL (see Section 9.1).
- Injection site pain (using a VAS; 100mm) by visit after self-injection using the assigned self-injecting device presentations at Baseline and Week 4
- Responses to post-injection SIAQ (versions 2.0 and 2.1) by visit following self-injection using the assigned self-injecting device presentations at Baseline and Week 4
- The structural and mechanical integrity of the bimekizumab-SS-1mL and the bimekizumab-AI-1mL after completion of self-injection using the assigned self-injecting device presentations
- The functional integrity of the bimekizumab-SS-1mL and the bimekizumab-AI-1mL after completion of self-injection using the assigned self-injecting device presentations

